2.4 Subject selection

2.4.1 General characteristics of the proposed subject population(s)

Male and female athletes, aged 18-25 years, will be recruited from athletic programs at collaborating study sites for Cohort 2.

2.4.2 Anticipated number of research subjects

Throughout the course of 18 months, the study will enroll 100 subjects in Cohort 2.

Cohort 2 will include 100 subjects; 50 Concussion Subjects (CCS) who have sustained an impact where concussion is highly suspected, as evidenced by impairment on either of the SCAT-3 domains: Symptom, Physical Signs, Orientation, Immediate Memory and 50 control subjects (CTR) who are teammates of the CCS and who did not experience impact, but who were participating in the same sport and session along with the injured CCS at the time of injury.

2.4.3 Inclusion criteria

- Athletes between the age of 18-25 years-old
- 20/30 or better eyesight (corrected vision allowed).
- English fluency.
- CCS - those who experience impact where concussion is highly suspected as evidenced by impairment in any of the SCAT-3 Domains: Symptoms, Physical Signs, Immediate Memory and Orientation. An Injured Athlete is concussed if he/she is FAIL on the Physical Signs, Score = 0 on the Orientation or Scoring below the cutoff scores on the Symptom Checklist and/or Immediate memory SCAT-3 domains.
 - Symptoms: Rating of 2 or higher on any of the following items:
 - Headaches
 - Nausea or Vomiting
 - Dizziness
 - Balance Problems
 - Blurred Vision
 - Feeling Slowed Down
 - Feeling like “in a fog”
 - “Don’t feel right”
 - Physical Signs:
 - Balance (Leg Stances): Number of Error(s) on any of the following 7 subtests classifies a subject as concussed.
 - I. Double Leg Stance: At least 3 errors
 - II. Single Leg Stance: At least 3 errors with either dominant or non-dominant foot
 - III. Tandem Stance: At least 3 errors or more.
 - Balance (Tandem Gait): FAIL on at least 2 of 4 trials:
 - I. FAIL per trial: more than 14 seconds to complete a trial

- II. FAIL per trial, if one or more of the following errors are made
 - a) If step off the line;
 - b) Separation between heel and toe
 - c) Touch/grab the examiner or an object
- Orientation: Score = 0 on any of the following 5 items
 - Date: Score = 0 (any date different from current)
 - Month: Score = 0 (any month different from current)
 - Day of the week: Score = 0 (any different from current)
 - Year: Score = 0 (any different from current)
 - Time: Score = 0 AND answer is MORE than + or – 1 hour apart from the correct time.
- Immediate Memory
 - Recall Total Score = less than 13 words recalled.
- CTR - a teammate of the CCS who did not experience impact but who was actively participating in the same sport and session along with the injured teammate at the time of injury

2.4.4 Exclusion criteria

- Clinical diagnosis of a neurological condition including the following: Stroke, Multiple Sclerosis, Epilepsy, Brain Tumor/Cancer, dyslexia, Nystagmus and/or Other major neurological condition.
- Clinical diagnosis of any of the following eye-sight abnormalities: Uncorrected Amblyopia, Uncorrected Myopia, Uncorrected Presbyopia, Uncorrected Farsightedness, Uncorrected Astigmatism.
- Psychiatric history with any of the following:
 - LIFETIME**
 - a. Clinical diagnosis of a Psychotic Disorder, Bipolar Disorder
 - b. Clinical diagnosis of ADHD or ADD
 - Within LAST YEAR**
 - c. Clinical diagnosis of Major Depressive Disorder
 - d. Clinical diagnosis of Substance Abuse Disorder
 - e. Clinical Diagnosis of Major Anxiety Disorder.
 - MEDICATION**
 - f. Use of a psychotropic medication
- Cannot have participated previously in any ETA-TV study visits (for instance, a subject that has completed any study visit as a control subject cannot participate as a concussed subject at a later time point).

2.5 Study Procedures

Post-concussion immediate and scheduled follow-up visits

Data Collection:

2.5.1 Visit 1

1. Visit 1 occurs immediately post-impact. The “Immediate” time frame for “post impact” is quantified as taking place as part of the naturalistic evaluation of the athlete suspected of sustaining a concussion. This will likely be immediately after the identification of a “hit” or other event that would lead to an athlete being evaluated for a possible concussion. At Visit 1, Level of Alertness, EYE-SYNC, DEM, ANAM-SRT, and SCAT-3: Symptom reporting, Physical Signs, Orientation, and Immediate Memory will be obtained (the above tests in combination will be referred to as ‘Testing Battery’).
 - a. Post-impact the subject undergoes EYE-SYNC measurement immediately at the sideline. EYE-SYNC to be performed 3 times consecutively.
 - b. Individuals enrolled as a Concussed Subject (CCS) are defined as those who experience impact where concussion is highly suspected as evidenced by impairment on any one of the SCAT-3 domains: Symptoms, Immediate Memory, Physical Signs or Orientation
 - c. For each CCS subject enrolled, immediately enroll a Control Subject (CTR). A CTR subject is defined as a teammate who did not experience impact, but who was actively participating in the same sport and session along with the injured teammate at the time of injury. The CTR subject also receives the Testing Battery. Prior to performing the Testing Battery, ensure the CTR subject meets the Inclusion and Exclusion criteria – Cohort 2 as per section 2.4.3 and 2.4.4.
 - d. CTR subject will complete Demographics during Visit 1.

2.5.2 Visits 2, 3 and 4

1. CCS must meet the inclusion and exclusion criteria prior to performing any assessments on Visit 2 (2 days post-injury). If CCS is ineligible, both CCS and CTR will discontinue participation in the study.
2. History of injury data for CCS and CTR subjects are collected during Visit 2.
3. Following CCS eligibility to continue participation in study, testing battery will be performed by both CCS and CTR.
4. During Visit 3 and Visit 4, all the assessments in the testing battery will be completed both by CCS and CTR.

The Day of injury is Day 1. Following visit 1, the testing battery will be collected for both the CCS and the CTR subject at three additional time points. Visit 2 will occur at 2 days post-injury. Visit 3 at 7 days post-injury (+/- 1 day), and Visit 4 at 14 days post-injury (+/- 3 days). It’s important that subjects are seen exactly at 2, 7, and 14 days post-injury. For instance, if subject sustains an injury on January 3, 2016 – Visit 2 will be on January 5th, visit 3 will be on January 10th and visit 4 will be January 17th.

The study windows are meant for unforeseen circumstances. Please notify the site Investigator for approval if the subject needs to be seen within the study window.

During all the visits in cohort 2 EYE-SYNC must be performed after administering level of alertness questionnaire and to be performed 3 times consecutively.

Please note: If a CTR subject sustains a concussion at any point while enrolled as a control, he/she will be withdrawn from the study and the paired CCS subject will continue on with the study visits without a CTR subject. The CTR subject will not be allowed to enroll as a CCS subject for the study.

If a CCS subject sustains a second concussion, he/she will be withdrawn from the study and the paired CTR subject will continue on with the study visits without a CCS subject.

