3.1.2 Planned Data Analysis and Sample Size Determination

Descriptive Statistics: We will provide descriptive statistics for all subjects included in our study. Specifically, for continuous variables such as age, and scores from DEM, ANAM-SRT, SCAT-3, and EYE-SYNC, we will provide means, medians, standard deviations and interquartile ranges. For categorical variables such as race, ethnicity and previous history of injury, we will present frequency distributions. We will utilize graphical tools such as histograms and box plots to describe distributions of continuous variables. If needed to adhere to modeling assumptions, we may consider transformations of outcomes, such as a log transformation.

Handling of Missing Data: We anticipate minimal missing data in this study. We expect that a small proportion of subjects recruited for the longitudinal study (1%) will not complete all visits. We will fully describe missing data for each variable and any pertinent patterns of missingness (e.g., how missingness is related to specific baseline measurements or time, if at all). The statistical methods we propose are particularly flexible for missing data and allow for systematic missingness that is related to observed features.

Statistical Tools for Each Aim: Our first aim addresses the integrity of data generated by EYE-SYNC. Specifically, in Aim 1A, we will characterize the feasibility of collecting and generating data in real-time as injuries occur by considering the proportion of time we are able to collect 3 subsequent measures using EYE-SYNC on the sideline in the field from a case using data from cases included in *Cohort 2* (described above). We deem EYE-SYNC to be a promising tool to be used on the field if we are able to make use of it 90% of the time. This will be tested using a one-sided exact binomial test. With 50 cases, we have excellent power to evaluate feasibility. More specifically if we use a decision rule such that we conclude EYE-SYNC to be a promising and practical tool to be used in the field if we have complete information on 40 of the 50 cases, we have over 95% power when the true rate of complete data is 90% with a type I error of 0.04 under the null hypothesis that an unacceptable rate of complete data is 70%.

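### Controls are withdrawn if concussed during follow-up, but no entry criterion screens them for a recent concussion outside the study

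*Combined protocol and SAP*

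**What the plan says.** **During follow-up.** Section 2.5.2 (Visits 2, 3 and 4) removes a control who becomes concussed: "If a CTR subject sustains a concussion at any point while enrolled as a control, he/she will be withdrawn from the study". It has a parallel rule for concussed subjects (CCS): "If a CCS subject sustains a second concussion, he/she will be withdrawn from the study". In both situations the partner continues unpaired.

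**At entry.** Section 2.4.3 defines the control (CTR) by the index session: "CTR - a teammate of the CCS who did not experience impact but who was actively participating in the same sport and session". Section 2.4.4 lists the neurological exclusions: "Clinical diagnosis of a neurological condition including the following: Stroke, Multiple Sclerosis, Epilepsy, Brain Tumor/Cancer, dyslexia, Nystagmus and/or Other major neurological condition". It also excludes eyesight and psychiatric conditions and psychotropic medication, and bars earlier participants: "Cannot have participated previously in any ETA-TV study visits". The synopsis has the same substance. None of these criteria names concussion.

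**When eligibility is checked.** Controls are checked at Visit 1 (Section 2.5.1): "Prior to performing the Testing Battery, ensure the CTR subject meets the Inclusion and Exclusion criteria". CCS are checked at Visit 2, and an ineligible CCS takes the paired control out of the study too (Section 2.5.2).

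**Injury history.** Section 2.5.2 gives the timing: "History of injury data for CCS and CTR subjects are collected during Visit 2". The only stated use is descriptive (Section 3.1.2): "For categorical variables such as race, ethnicity and previous history of injury, we will present frequency distributions".

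**The concern.** Aim 2 compares EYE-SYNC trajectories of injured and non-injured athletes, and Section 3.1.1 makes that comparison part of the primary endpoint. The comparison needs controls who are free of concussion effects. The plan protects this after enrolment but not before it. An athlete concussed shortly before the index session, outside the study and now back in play, meets every control criterion.

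If such an athlete still has residual effects, the control group mean moves toward the case mean and the contrast shrinks. The analysis as written would not detect this. The schedule in Section 2.3.2 shows no EYE-SYNC measurement before injury, so a control's residual impairment cannot be judged against that athlete's own baseline. The mixed models in Section 3.1.2 allow for correlation within subjects and within pairs, which does not correct a misclassified control.

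**Working it through.** **1. Is there a rule that closes the gap?** The documents state no figure on this point to reproduce, so the first check is of the text.

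| Provision | Does it stop a recently concussed control? |
|---|---|
| Control definition (2.4.3) | No. It concerns impact in the index session |
| SCAT-3 cutoffs (2.4.3) | No. They define CCS; no rule requires a control to be unimpaired on them |
| Neurological exclusion (2.4.4) | Not stated. Concussion is not named and there is no look-back |
| Earlier study visits (2.4.4) | In part. It stops athletes whose earlier concussion was tested in this study, and no others |
| Taking part in the session (2.4.3) | In part. It implies return to play, but no clearance or symptom-free status is required |
| Loss of eligibility as a withdrawal reason (3.0.1) | No. Recent concussion is not an eligibility criterion |
| Injury history (2.5.2, 3.1.2) | No. It is taken after Visit 1 testing and used only descriptively |

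The gap is therefore real but partly closed. Section 2.4.4 does use a look-back of one year for three psychiatric diagnoses, so the device is already part of the plan.

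**2. How large could the effect be?** Let Δ be the true case-control difference, c the share of controls with residual effects, and f the fraction of the case-level effect that they carry. Both c and f are assumptions, since the documents give neither.

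- Expected control shift: c × f × Δ
- Expected difference: Δ − c × f × Δ = Δ(1 − cf)
- Relative N for the same power: 1/(1 − cf)²

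| c | Controls out of 50 | Difference kept, f = 1 | Extra N, f = 1 | Difference kept, f = 0.5 | Extra N, f = 0.5 |
|---|---|---|---|---|---|
| 2% | 1 | 98% | 4% | 99% | 2% |
| 5% | 2.5 | 95% | 11% | 97.5% | 5% |
| 10% | 5 | 90% | 23% | 95% | 11% |
| 20% | 10 | 80% | 56% | 90% | 23% |

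For example, at c = 10% and f = 1, 1/(0.90)² = 1.235.

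**3. What would that do to power?** Section 3.1.2 gives no effect size, standard deviation or power for Aim 2. As an illustration, take 50 per group, two-sided 0.05, an unpaired comparison at one time point and an assumed standardised difference of 0.57. At f = 1, power is 81% with no affected controls, 77% at c = 5%, 73% at 10% and 63% at 20%.

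**4. Level or trajectory?** The formula applies visit by visit, with f allowed to change. If the residual effect fades over the four visits, it reduces the trajectory contrast. If it is a constant offset, it cancels in the change between visits and reduces only the difference in level.

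**5. What is not affected?** The Aim 1A feasibility test uses cases only, so its decision rule does not depend on this point.

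**The case against.** The strongest reply is that the two sets of rules do different jobs. The withdrawal rules deal with a subject whose status changes in mid-series: a newly concussed control is no longer a control, and a second concussion upsets a visit schedule counted from the index injury. Neither rule implies a view on earlier concussions. This stands. A reader might infer that the entry criteria contradict the withdrawal rules, or that the plan means to exclude cases with an earlier concussion. The documents say neither.

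The second reply is rarity. A control has to be playing and cannot have had an earlier study visit. A site might also read the general neurological exclusion as covering an unresolved concussion. What remains is a concussion that the study did not capture, with effects that outlast return to play, in the teammate chosen as control. This stands as a limit on size but does not close the gap, because neither clearance nor freedom from symptoms is required.

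The third reply concerns cases. A reader might want the same exclusion for CCS. That is a debatable choice of scope for a tool meant for athletes with suspected concussion. It is also costly, because a CCS found ineligible at Visit 2 discontinues the pair after Visit 1 testing. The direction of bias is not established either: an unresolved earlier concussion blurs the start of the recovery curve, and could make Visit 1 worse and widen the difference. This objection stands in full.

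Lastly, the study calls itself a feasibility and exploratory study. That lowers the stakes, but the injured versus non-injured comparison is still part of its primary endpoint.

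**Conclusion.** The point holds for controls, as an inexpensive improvement. Nothing in Sections 2.4.3 or 2.4.4 screens controls for a recent concussion outside the study, and the history taken at Visit 2 changes neither eligibility nor analysis. The expected bias from such controls is toward a smaller Aim 2 difference.

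The size is unknown and probably small. The shares of 2% to 20% are assumptions, and f = 1 is an upper case in which a returned athlete performs like an acutely injured one. At half that effect, the loss for shares of 2% to 10% is 1% to 5%.

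The table should not be read as evidence that recovering controls are common, since the documents give no frequency. Nor should the 14-day follow-up be read as a recovery period: it is the timing of the last visit, and the documents do not call it anything else. No stated sample size, power or type I error changes.

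**What to change.** **Controls.** Add one line to Section 2.4.4, for CTR only, excluding a concussion within a look-back period before the index session. The investigators should fix the period in advance. The 14-day follow-up span is one natural reference, with the caveat given in the verdict. Ask the question at the eligibility check that Section 2.5.1 already requires before the control's Visit 1 testing. The cost is one exclusion line and one question; an occasional teammate will be ineligible and another will serve as control.

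**Cases.** Leave CCS entry unchanged. Pre-specify in Section 3.1.2 a sensitivity analysis of Aim 2 without cases who had a recent earlier concussion, and state whether their paired controls stay in the model. The cost is a sentence or two in the analysis plan. It works only if the Visit 2 history item records dates. That form is not in the documents, so the sponsor should confirm this.

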3.0.1 Withdrawal of subjects

If a subject first agrees to participate and then changes his/her mind, the subject is free to withdraw consent and discontinue participation at any time. The subject's decision will not affect his/her ability to receive medical care and the subject will not lose any benefits to which he/she would otherwise be entitled.

If a subject decides to withdraw consent to participate in this study, the subject should notify the site Investigator. The subject may ask to have their data withdrawn from the study database. The subject has the right to refuse to allow his/her data to be studied now or saved for future study.

The Protocol Director may also withdraw a subject from the study without consent for one or more of the following reasons:

- Failure to follow the instructions of the Protocol Director and study staff (non-compliance).
- The Protocol Director decides that continuing participation could be harmful to the subject.
- Pregnancy
- The subject becomes no longer eligible to complete follow-up sessions due to no longer meeting eligibility requirements.
- Need of treatment not allowed in the study.
- The study is cancelled.
- Other administrative reasons.
- Unanticipated circumstances.

If subjects are withdrawn from the study due to non-compliance or protocol director decision the subject will have the option to withdraw the data.

3.1 Study Outcome Evaluations

3.1.1 Study endpoints

Our primary endpoint will be the acquisition of sufficient data to establish integrity and reliability of EYE-SYNC data and to compare and characterize trajectories of EYE-SYNC measurements in injured versus non-injured athletes.

Our secondary endpoint will be to characterize interrelationships among variables relevant to concussion including DEM, ANAM-SRT, and SCAT-3 scores with EYE-SYNC.

If subjects are withdrawn from the study due to non-compliance or Protocol Director decision the subject will have the option to withdraw the data as described above.

3.1.2 Planned Data Analysis and Sample Size Determination

Descriptive Statistics: We will provide descriptive statistics for all subjects included in our study. Specifically, for continuous variables such as age, and scores from DEM, ANAM-SRT, SCAT-3, and EYE-SYNC, we will provide means, medians, standard deviations and interquartile ranges. For categorical variables such as race, ethnicity and previous history of injury, we will present frequency distributions. We will utilize graphical tools such as histograms and box plots to describe distributions of continuous variables. If needed to adhere to modeling assumptions, we may consider transformations of outcomes, such as a log transformation.

Handling of Missing Data: We anticipate minimal missing data in this study. We expect that a small proportion of subjects recruited for the longitudinal study (1%) will not complete all visits. We will fully describe missing data for each variable and any pertinent patterns of missingness (e.g., how missingness is related to specific baseline measurements or time, if at all). The statistical methods we propose are particularly flexible for missing data and allow for systematic missingness that is related to observed features.

Statistical Tools for Each Aim: Our first aim addresses the integrity of data generated by EYE-SYNC. Specifically, in Aim 1A, we will characterize the feasibility of collecting and generating data in real-time as injuries occur by considering the proportion of time we are able to collect 3 subsequent measures using EYE-SYNC on the sideline in the field from a case using data from cases included in *Cohort 2* (described above). We deem EYE-SYNC to be a promising tool to be used on the field if we are able to make use of it 90% of the time. This will be tested using a one-sided exact binomial test. With 50 cases, we have excellent power to evaluate feasibility. More specifically if we use a decision rule such that we conclude EYE-SYNC to be a promising and practical tool to be used in the field if we have complete information on 40 of the 50 cases, we have over 95% power when the true rate of complete data is 90% with a type I error of 0.04 under the null hypothesis that an unacceptable rate of complete data is 70%.

The goal of Aim 2 is to assess whether data from EYE-SYNC correlates with clinically meaningful endpoints. To that end, we will create *Cohort 2* by collecting data (in replicates of 3) Immediately Post Impact, 2 days from injury, 7 days from injury and 14 days from injury from 50 cases (defined as those who experience impact where concussion is highly suspected) and 50 matched controls (a teammate who did not experience impact but who was participating in the same sport and session along with the injured teammate at the time of injury). Using mixed effects regression techniques, we will examine whether the trajectory of EYE-SYNC changes over time for those injured differs significantly from those who were not injured. In addition, we will characterize trajectories of change in EYE-SYNC over time for those injured and for athletes who are injury free. Such models account for the correlation of scores within a subject over time as well as for the matched pairing of cases and their corresponding teammates. In addition, such models are robust to assumptions regarding missing data.

The goal of Aim 3 is to describe interrelationships among relevant variables used to describe concussion and EYE-SYNC. This aim is fairly exploratory but will pave the way for future studies. We will rely on mixed effects techniques to characterize relationships of interest

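### Aim 1A is worded as a test of 90% usability, but the test is against 70%, and the printed cut-off of 40 of 50 does not have the stated type I error of 0.04

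*Combined protocol and SAP*

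**What the plan says.** The text is in section 3.1.2, Planned Data Analysis and Sample Size Determination, and is repeated in the synopsis under Statistical Tools for Each Aim.

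- **Endpoint:** "the proportion of time we are able to collect 3 subsequent measures using EYE-SYNC on the sideline in the field from a case", using the Cohort 2 cases.
- **Criterion in words:** EYE-SYNC is deemed a "promising tool to be used on the field if we are able to make use of it 90% of the time".
- **Link to the test:** the next sentence reads "This will be tested using a one-sided exact binomial test".
- **Decision rule:** the device is concluded to be a "promising and practical tool to be used in the field if we have complete information on 40 of the 50 cases".
- **Operating characteristics:** "we have over 95% power when the true rate of complete data is 90" per cent, with a "type I error of 0.04 under the null hypothesis that an unacceptable rate of complete data is 70" per cent.

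Neither place says whether exactly 40 is a pass. Neither gives a confidence interval or a minimum observed rate for Aim 1A, or says what a pass establishes about the 90% figure.

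**The concern.** Read in order, the sentences present 90% usability as the hypothesis under test. The test that follows cannot address it. Rejecting a null of 70% is evidence for a rate above 70% and for nothing higher; 90% enters only as the rate at which power is calculated. The rule then awards the favourable label at an observed 80%.

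The boundary adds a second difficulty. If 40 of 50 is a pass, that result has to reject 70% at the stated level for even the weaker conclusion to follow.

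Aim 1A is listed under the primary objectives and is the only analysis in the plan with a numerical decision rule, a type I error and a power. A reader of the final report could take a pass as showing that sideline collection works nine times in ten, when the test supports a much weaker statement. At exactly 40 of 50, it would not support even that at the stated error rate.

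**Working it through.** **Inputs, all from section 3.1.2.** n = 50 cases; null rate p0 = 0.70; design alternative p1 = 0.90; one-sided exact binomial test; printed cut-off 40; stated type I error 0.04; stated power over 95%.

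**Formula.** With X the number of cases with complete data and r the lowest passing count,

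P(pass | p) = P(X ≥ r | p) = Σ from k = r to 50 of C(50, k) p^k (1 − p)^(50 − k).

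Type I error is this sum at p = 0.70, and power is the sum at p = 0.90.

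**Step 1: reproduce the plan's figures.**

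| Lowest passing count | Observed rate | Type I error (p = 0.70) | Power (p = 0.90) |
|---|---|---|---|
| 40 | 80% | 0.0789 | 0.9906 |
| 41 | 82% | 0.0402 | 0.9755 |
| Stated | – | 0.04 | over 0.95 |

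A pass at 40 or more satisfies the power statement but has about twice the stated type I error (0.0789 / 0.04 ≈ 2.0). A pass at more than 40, that is 41 or more, matches both stated figures. A normal approximation does not rescue the printed cut-off: (40 − 35) / √(50 × 0.7 × 0.3) = 5 / 3.24 = 1.54 gives 0.061, and 4.5 / 3.24 = 1.39, with continuity correction, gives 0.082.

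**Step 2: what the lowest passing result shows about 70%.** The one-sided exact p-value against 70% equals the type I error in the table. It is 0.079 at 40 of 50, which rejects 70% at neither 0.04 nor 0.05. At 41 of 50 it is 0.0402, which agrees with the stated 0.04 after rounding.

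**Step 3: what a pass says about rates between 70% and 90%.**

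| True rate | P(pass), ≥ 40 | P(pass), ≥ 41 |
|---|---|---|
| 75% | 0.26 | 0.16 |
| 80% | 0.58 | 0.44 |
| 85% | 0.88 | 0.79 |
| 90% | 0.99 | 0.98 |

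Devices well short of 90% pass often under either boundary.

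**Step 4: how specific results sit against 90%** (exact Clopper-Pearson 95% intervals).

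| Result | 95% interval | P(X ≤ x given 0.90) |
|---|---|---|
| 40/50 | 66.3% to 89.97% | 0.0245 |
| 41/50 | 68.6% to 91.4% | 0.058 |
| 45/50 | 78.2% to 96.7% | 0.57 |

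Only the single result 40 of 50 lies significantly below 90%, and only just: the upper limit is 0.8997, and the Wald interval (68.9% to 91.1%) includes 90%. From 41 upward no passing result is significantly below 90%. Even 45 of 50 does not establish 90%, since its interval extends down to 78.2%.

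**The case against.** The strongest defence is that this is a conventional single-arm design: an unacceptable rate of 70%, a target of 90%, and a cut-off between them. A cut-off below the target is how such a design obtains its power; requiring an observed 90% (45 of 50) would reduce power at a true 90% to 0.62. Null, alternative, sample size and cut-off are all disclosed, the study is described as feasibility and exploratory, and the label attached to a pass does not itself claim that 90% has been shown. All of this stands as a defence of the design. It does not defend the sentence that says the 90% criterion is what will be tested, and it does not repair the mismatch between a cut-off of 40 and a type I error of 0.04.

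Two stronger readings are tempting, and the documents support neither.

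- A reader might infer that a pass contradicts 90% usability. That is true only at exactly 40 of 50, a result with probability 0.9906 − 0.9755 = 0.015 at a true 90% and 0.5836 − 0.4437 = 0.14 at a true 80%. Under the boundary of 41 that reproduces the stated figures, 40 is a fail and the argument disappears.
- A reader might infer that the plan has two conflicting cut-offs, 40 and 45, so that counts of 40 to 44 both pass and fail. No 45-of-50 rule appears in the plan. The 90% is used there as a true rate, and a true rate is not a minimum observed count.

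**Conclusion.** The concern holds as a fault of wording and of boundary, not of design. The plan presents 90% as the tested criterion when the test is against 70%, so a pass supports at most a complete-data rate above 70%. The size of the gap is that a device with a true rate of 80% passes with probability 0.58 (cut-off 40) or 0.44 (cut-off 41). Separately, the printed cut-off, read as 40 or more, has type I error 0.079 rather than 0.04; 41 or more gives 0.0402 with power 0.9755. That second figure depends on the reading of 40 as a pass. If the authors meant more than 40, their figures are right and only the sentence is wrong.

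The calculations assume 50 evaluable cases, independent of one another, with a common probability of complete data.

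**What to change.** Make the same changes in section 3.1.2 and in the synopsis:

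1. State the boundary as at least 41 of 50, which keeps the stated 0.04 and power over 95%. Alternatively, keep 40 and restate the type I error as 0.079.
2. State that 70% is the unacceptable rate being tested and that 90% is the design alternative used for power.
3. State that a pass at 41 or more supports a rate above 70%, not a rate of 90%. If 40 is kept, the statement about exceeding 70% must carry the 0.079 error rate.
4. Report the observed rate with its exact 95% confidence interval beside the 90% target. At exactly 41 the two-sided interval starts at 68.6% although the one-sided test passes, so note that the test is one-sided (the lower limit of the exact 90% interval is 70.7%).

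No minimum observed rate of 90% needs to be added.

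The cost is a few sentences; sample size, data collection and test are unchanged. Moving from 40 to 41 lowers power at a true 90% from 0.9906 to 0.9755, still above the stated 95%. The real price is that the claim a pass supports becomes less favourable.

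### The feasibility rule of 40 out of 50 cases has an exact one-sided type I error of 0.079, not the stated 0.04; the stated figure belongs to a cut-off of 41

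*Combined protocol and SAP*

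**What the plan says.** Section 3.1.2 (Planned Data Analysis and Sample Size Determination) covers Aim 1A, the feasibility of obtaining three EYE-SYNC measurements at the sideline from each case. The synopsis repeats the text under Statistical Tools for Each Aim. The paragraph makes these statements:

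- The device is considered promising "if we are able to make use of it 90% of the time".
- The method named is an exact binomial test of a single proportion, one-sided.
- On the sample size, the plan's claim is: "With 50 cases, we have excellent power to evaluate feasibility".
- Success is declared "if we have complete information on 40 of the 50 cases".
- Power is put at over 95% for a true completeness rate of 90%, "with a type I error of 0.04" for a null rate of 70%, which the plan calls unacceptable.

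Neither place says whether 40 itself counts as success, and neither uses wording such as more than 40 or at least 41. Aims 2 and 3 have no power or sample-size calculation.

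**The concern.** A cut-off, a sample size and a null rate fix the type I error of an exact binomial test completely. The plan gives all three and also states the error rate, so the statement can be checked without any assumption about data. On the natural reading, where 40 complete cases are enough, the error rate does not follow from the rule.

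This matters for two reasons. Aim 1A is part of a primary objective, and this calculation is the only statistical justification the plan gives for its sample size. Also, a go/no-go rule has to be unambiguous before data are seen. If exactly 40 of 50 cases were complete, the rule would declare success while the test named in the same paragraph would give p = 0.079, above the only error rate the plan states. Choosing between 40 and 41 at that point would be a post hoc decision.

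**Working it through.** **Inputs**, all from Section 3.1.2: n = 50 cases; one-sided exact binomial test of one proportion; null rate p0 = 0.70; alternative rate p1 = 0.90; rule r = 40; stated type I error 0.04; stated power over 95%.

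**Formulas.** With X the number of cases with complete data and success declared at X ≥ r:

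- type I error = P(X ≥ r | n = 50, p = 0.70) = Σ from x = r to 50 of C(50, x) · 0.70^x · 0.30^(50−x)
- power = P(X ≥ r | n = 50, p = 0.90), the same sum with 0.90 and 0.10

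**Results.**

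| Success if X is at least | Type I error at 70% | Power at 90% | Agrees with 0.04 and over 95%? |
|---|---|---|---|
| 39 | 0.1390 | 0.9968 | no, type I error too high |
| 40 (as written) | 0.0789 | 0.9906 | no, type I error too high |
| 41 | 0.0402 | 0.9755 | yes, both |
| 42 | 0.0183 | 0.9421 | no, power below 95% |

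The plan's two figures are therefore reproduced at 41 and only at 41. The rule as written has 0.0789/0.04 = 1.97 times the stated error. The whole excess is the probability of exactly 40 complete cases at a true rate of 70%: 0.0789 − 0.0402 = 0.0386 from unrounded values.

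**Could another method give 0.04 at a cut-off of 40?**

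- Normal approximation: 0.0614 without and 0.0825 with continuity correction.
- Mid-p: 0.0595.
- Two-sided exact: 0.164.
- z statistic with the standard error taken at the observed 80%: 0.10/√(0.8 × 0.2/50) = 1.77, tail 0.0385. This rounds to 0.04 but is not the exact test the plan names.
- Half of 0.0789 is 0.0394, but there is no basis for halving a tail that is already one-sided.

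**How often the two cut-offs disagree.** They differ only when X = 40. That probability is 0.039 at a true rate of 70%, 0.140 at 80% and 0.015 at 90%.

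**Intervals at the boundary (Clopper-Pearson).**

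| Result | Two-sided 95% interval | One-sided 95% lower bound |
|---|---|---|
| 40/50 | 66.3% to 90.0% | 68.4% |
| 41/50 | 68.6% to 91.4% | 70.7% |

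The two-sided 95% interval includes 70% at both results, so it does not separate the two cut-offs. The one-sided bound corresponds to a one-sided test at 0.05 and does separate them: it is below 70% at 40 and above 70% at 41.

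**The case against.** The strongest reply is that the authors meant more than 40. Both stated figures then hold exactly as given (0.0402 and 97.5%), the design calculation was right, and only the wording slipped. This is probably what happened. It does not leave the text correct: the rule as worded treats 40 as sufficient, and nothing in either place says otherwise. On one reading the cut-off has to change, and on the other the error rate has to change.

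A second reply concerns importance. The study calls itself a feasibility and exploratory study, the conclusion is only that the tool is promising and practical, the power claim holds at either cut-off, and the two rules part company only at exactly 40 of 50. These points stand and limit the practical damage. Against them, this is a primary aim and the plan's only powered test, and if the true rate is 80% the ambiguous result has about a 14% chance of occurring.

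Third, the plan names no 0.05 level; 0.04 is its only error rate. That is correct, and the conclusion does not depend on the choice, since 0.079 exceeds both.

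Finally, the two-sided 95% interval at 40/50 is weak evidence against that cut-off, because the interval at 41/50 also contains 70%. This is also right. The case rests on the exact tail probabilities, not on that interval.

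**Conclusion.** The concern holds. Applied as written, with 40 of 50 counted as success, the rule has an exact one-sided type I error of 0.0789 against a stated 0.04, a factor of 1.97. The stated error rate and power together identify a cut-off of at least 41 (0.0402 and 97.5%). The doubling depends on reading the rule as 40 or more. If the sponsor meant more than 40, the stated figures stand and the wording of the rule is the error. The text needs correcting in either case, and before the data are examined. The calculation assumes 50 evaluable cases with independent outcomes, as the plan's own binomial test does. The adequacy of 50 cases for this test is not in question, because power exceeds 95% at both cut-offs.

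**What to change.** In Section 3.1.2 and in the matching synopsis text, state the rule as complete information on at least 41 of the 50 cases, with type I error 0.040 and power 97.5% at a true rate of 90%. The cost is one number in two places. The bar rises by one case, power falls from 99.1% to 97.5%, and n stays at 50. The alternative is to keep 40 and restate the type I error as 0.079 and the power as 99.1%.

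Three additions would help but are separate from the arithmetic:

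- State the nominal level of the test, and say that the exact test at that level decides if the number of evaluable cases is not 50. At one-sided 0.05, for example, the requirement is 40 of 49, 41 of 50 or 42 of 51. A nominal level of exactly 0.04 would not do, because 41 of 50 has p = 0.0402.
- Report the observed rate with a one-sided 95% lower bound or a two-sided 90% interval, so that the interval matches the one-sided test.
- Word a positive conclusion as a rate above 70%. That is the hypothesis tested; passing at 41 of 50 (82%) does not show that the 90% in the plan's opening criterion has been reached.
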